9.5 End of IP treatment

Subjects that complete the planned treatment portion of the study will have move into the follow up period.

9.5.1 Follow up

Visit 5- First follow up visit (28 +/- 7 days)

- Vital signs
- Review con meds
- Assess for any Adverse Events
- Skin exam limited to all target lesions
- Photograph and measure target lesions (Appendix A)
- Schedule the next follow up visit in 4 weeks.

Visit 6- Second follow up visit (28 +/- 7 days)

- Vital signs
- Review con meds
- Assess for any Adverse Events
- Skin exam limited to all target lesions
- Photograph and measure target lesions (Appendix A)
- Schedule second ultrasound to be completed on TILs before next follow up visit
- Schedule the next follow up visit in 6 weeks.

Visit 7- Third follow up visit (42 +/- 10 days)

- Vital signs
- Review concurrent meds

- Assess for any Adverse Events
- Skin exam limited to all target lesions
- Photograph and measure target lesions (Appendix A)
- Schedule the next follow up visit in 14 weeks.

Visit 8 - Fourth follow up visit (98 +/- 21 days)

- Vital signs
- Review con meds
- Assess for any adverse events
- Skin exam limited to all target lesions
- If sites are free of disease, participant participation will be complete
- Photograph and measure target lesions (Appendix A)
- Complete subject payment form

Visit 9 – Telephone Follow up (356 +/- 31 days) after Visit 1

• Assess for changes of target lesions

• If active lesion(s) are noted by the participant, they will follow up with a dermatologist and their records will be requested

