- Inject 0.1ml 4ml (based on TILs size) and number of lesions selected.
 Talimogene laherparepvec at nominal concentration of 10⁸ PFU/mL with approximately 1.15 mL in a 2 mL vial for the subsequent doses.

Visit 4: Fourth injection visit: Two (2) Weeks after V3

- Target lesions are identified and documented with measurements and photographs. Photographs will be taken with global and close up view of the anatomical area and lesion (Appendix A).
- Inject 0.1ml 4ml (based on TILs size) and number of lesions selected.
 Talimogene laherparepvec at nominal concentration of 10⁸ PFU/mL with approximately 1.15 mL in a 2 mL vial for the subsequent doses.

Visit 5: First Follow up visit: Four (4) weeks after V4

 Target lesions are identified and documented with measurements and photographs. Photographs will be taken with global and close up view of the anatomical area and lesion (Appendix A).

Visit 6: Second Follow up visit: Four (4) weeks after V5

 Target lesions are identified and documented with measurements and photographs. Photographs will be taken with global and close up view of the anatomical area and lesion (Appendix A). A repeat high-frequency ultrasound of target lesions will be completed to assess response from baseline.

Visit 7: Third Follow up visit: Six (6) weeks after V6

• Target lesions are identified and documented with measurements and photographs. Photographs will be taken with global and close up view of the

anatomical area and lesion (Appendix A).

Visit 8: Fourth Follow up visit: Fourteen (14) weeks after V7

• Target lesions are identified and documented with measurements and photographs. Photographs will be taken with global and close up view of the anatomical area and lesion (Appendix A).

Visit 9: Telephone Follow up: twelve (12) months after first injection (V1)

• Research coordinator will assess patient over the phone to determine if any changes have occurred to target lesions after V8.

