- Assess for any adverse events
- Skin exam only of target lesions
- Photograph and measure all target lesions (Appendix A)
- Ultrasound of TILs at Radiology Department for follow-up evaluation(Appendix B)
- Schedule the third follow up visit in 6 weeks

Visit 7- Third follow up visit (42 +/- 10 days)

- Vital signs
- Review con meds
- Assess for any adverse events
- Skin exam only of target lesions
- Photograph and measure all target lesions (Appendix A)
- Schedule the next follow up visit in 14 weeks.

Visit 8 - Fourth follow up visit (98 +/- 21 days)

- Vital signs
- Review con meds
- Assess for any adverse events
- Skin exam only of target lesions
- Photograph and measure all target lesions (Appendix A)

Visit 9 – Telephone Follow up (356 +/- 31 days) after Visit 1

- Assess for changes of target lesions
- If active lesion(s) are noted by the participant, they will follow up with a dermatologist and their records will be requested

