9.4 Study Assessments

9.4.1 Tumor Measurements:

Tumor measurements will be done at each visit. Imaging assessment with high frequency ultrasound will be done at baseline and at the second follow-up visit (Visit 6). At baseline, up to 5 TILs that are at least 10cm apart will be selected to be followed over the course of the study. Up to 10 TNILs can be followed with no more than 2 TNILs selected in the same anatomical area as a TIL. Responses in TILs and TNILs will be measured serially. Clinical measurements will be performed with a millimeter measuring tape (Appendix A). All measurements will be selected that will be able to be followed clinically and for ultrasound evaluations. The RECIST 1.1 (Appendix B) response criteria will be used to evaluate tumor response. Individual tumor measurements will also be conducted to determine clinical management of TILs and TNILs. The timeframe for the clinical (primary endpoint) and evaluation will be at Visit 6 and for high-frequency ultrasound (secondary endpoints) at Visit 6 as well.

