	 injections will be given to TILs who have achieved IL-CR prior to the 4th injection visit If recurrent at any 	Visit 6 or beyond, alternative therapeutic intervention will be offered	 If subject has additional TILs, will continue study participation If subject has only one, subject will be 	intervention will be offered if no IL-CR or IL-PR is observed by Visit 6.
TILs	point after IL-CR has been documented, then alternative therapeutic intervention offered (surgical excision, radiation, intralesional therapy etc.) based on patient preference	• If IL-PR continues, TIL will be closely followed until Visit 8, where alternative therapeutic intervention will then be offered	 withdrawn If IL-RPD occurs, treatment will be deferred that visit and will be reevaluated next visit. o If IL-PD confirmed, lesion withdrawn from study and alternative 	
			therapeutic intervention ○ If subject has more than one TIL, then lesions will continue to be a part of the study	
TNILs	 IL-CR to be determined at the latest by Visit 6 (8 week follow up), and will be followed for 6 	• IL-PR will be followed and assessed up to Visit 6 (8 week follow up)	 IL-PD at Visit 3 will undergo alternative therapeutic intervention 	 IL-SD will be followed and assessed up to Visit 6 (8 week follow up)
	monthsIf recurrent at any	 Alternative therapeutic 		 Alternative therapeutic

Table 7. Management of individual TILs and TNILs

point after IL-CR ha	s intervention will	intervention will
been documented a	It be offered if no	be offered if no
Visit 6, then	IL-CR is	IL-CR is
alternative	observed by	observed by
therapeutic	Visit 6	Visit 6
intervention offered		

9.4.2 High Resolution Ultrasonography of Squamous Cell Cancer:

The subjects will complete ultrasound assessments of their lesions at screening Visit (0), and at Visit 6 (second follow up visit).

METHOD:

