26. STUDY SCHEDULE

Test or Procedure	Screening Visit 0	Treatment Visit 1	Treatment Visit 2	Treatment Visit 3	Treatment Visit 4	Follow-up 1- Visit 5	Follow-up 2 Visit 6	Follow-up 3 Visit 7	Follow- up 4 Visit 8	Telephone Follow-up	Early Term Visit
Informed consent	Х										
Medical history ¹	Х										
Concurrent meds	Х	Х	Х	Х	Х	Х	Х	Х	Х		х
Vital Signs	Х	Х	Х	Х	Х	Х	Х	Х	Х		Х
Physical Exam	Х										
Hematology ²	Х			Х							Х
Serum chemistry ³	Х			Х							х
Urine or serum pregnancy test	х										
Tumor evaluation ⁴	Х	Х	Х	Х	Х	Х	Х	Х	Х		х
Tumor Ultrasound after visit ⁵	х						х				
Skin biopsy	Х										
Adverse event evaluation ⁶		Х	Х	Х	Х	Х	Х	Х	Х		х
IPTreatment Intervention Device (syringe)		Х	Х	Х	Х						
Telephone Assessment ⁷										X	

1 = Complete medical history will include demographics

2 = Hematology to include CBC, differential and platelet count

3 = Chemistry to include chemistries, liver function tests

4 = Tumor measurements, photographs

5 = Tumor ultrasound will only be performed for patients enrolled at UACC

6 = AE recording will begin on Visit 1 of the IP treatment/intervention/device

7 = Verbal assessment of changes of target lesions

27. GLOSSARY - Not applicable

28. DEFINITIONS- Not applicable

29. **REFERENCES**

5. Jesitus J. Lower-leg wound healing requires creativity, skill. Dermatology Times [Internet]. 2011 [cited 2017. Available from:

http://dermatologytimes.modernmedicine.com/dermatology-

times/news/modernmedicine/modern-medicine-feature-articles/lower-leg-woundhealing-requi

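### Section 9.5.1 lets the response ultrasound run until Visit 7 while other sections fix it at Visit 6, so it can follow alternative treatment or lag the clinical reading by weeks

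*Combined protocol and SAP*

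**What the plan says.** Most of the protocol puts the second ultrasound at Visit 6, eight weeks after the last injection:

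- Section 2.4, Table 1, under Visit 6: "A repeat high-frequency ultrasound of target lesions will be completed to assess response from baseline".
- Section 9.3 lists the radiology scan of the TILs among the Visit 6 procedures.
- Section 9.4.1 sets Visit 6 as the time of the clinical primary assessment and adds "for high-frequency ultrasound (secondary endpoints) at Visit 6 as well".
- Section 9.4.2 names Visit 6 twice. One of the two sentences calls it the first follow-up visit, although it is the second.

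Two places differ or are looser:

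- Section 9.5.1, under Visit 6: "Schedule second ultrasound to be completed on TILs before next follow up visit". The next follow-up visit is Visit 7.
- Section 26 marks the scan under Visits 0 and 6, but the row is labelled "Tumor Ultrasound after visit" and carries no day limit.

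Table 7 (Section 9.4.1.2) makes Visit 6 a decision point for each lesion. For a TIL with stable disease, alternative "intervention will be offered if no IL-CR or IL-PR is observed by Visit 6". A TIL with progressive disease at Visit 6 is withdrawn and treated otherwise.

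Section 16.1.2, item 6, calls for the ultrasound response rate and its correlation with the clinical rate. Sections 16.2.1 to 16.2.8 give no analysis for this endpoint. Sections 1.3 and 26 restrict the scan to patients enrolled at the University of Arizona Cancer Center.

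**The concern.** The ultrasound endpoint is informative only if both methods look at the same lesion in the same state. Staff who follow 9.3 scan at Visit 6. Staff who follow 9.5.1 comply with the protocol by scanning just before Visit 7. Both instructions cannot govern.

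The later window opens exactly when lesions without clinical response become eligible for another treatment. If such a lesion is removed or treated first, a later scan no longer describes the effect of the study drug. If it is not scanned at all, the result is missing. Even with no other treatment, a lesion can shrink or regrow over six weeks, so disagreement between the two methods is mixed with elapsed time. At stake is the validity of one secondary endpoint.

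**Working it through.** **1. Length of the gap.** Inputs: Visit 7 is six weeks after Visit 6 (Section 2.4, Table 1), with a window of 10 days either way (Sections 9.5.1 and 9.7).

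- Nominal interval: 6 × 7 = 42 days, which matches the protocol's figure.
- Range counted from the actual Visit 6: 42 − 10 = 32 to 42 + 10 = 52 days.
- Gap between the clinical reading and the scan: 0 days if the scan is done at Visit 6. Under 9.5.1 it is nominally up to 42 days, and at most about 52.
- If both visits were instead pinned to a fixed calendar, with Visit 6 seven days early and Visit 7 ten days late, the limit would be 42 + 7 + 10 = 59 days. Table 1 counts from Visit 6, so 52 is the better reading.

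Measured from the last injection, Visit 6 falls nominally at 28 + 28 = 56 days. A scan on the eve of Visit 7 would fall at about 56 + 42 = 98 days.

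**2. Overlap with alternative treatment.** By Visit 6 status in Table 7:

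- Complete or partial response: alternative treatment is not offered at Visit 6, so only elapsed time matters.
- Stable disease: alternative treatment is offered from Visit 6, with no date attached. This is the clear route to a post-treatment scan.
- Progressive disease: the lesion is withdrawn and treated. The documents do not say whether a withdrawn TIL is still scanned, so the result is either a post-treatment scan or a missing one.

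No section requires the scan before alternative treatment, excludes a later scan, or caps the days between the two readings.

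**3. Effect on the ultrasound response rate.** Take the endpoint at subject level. Let N subjects be due a scan, and let R be those who would be ultrasound responders at Visit 6. Suppose m subjects are treated otherwise before the scan, and k of these m would have been ultrasound responders at Visit 6. The intended rate is R/N.

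| How the m subjects are counted | Reported rate | Direction |
|---|---|---|
| Post-treatment scan read as response | (R + m − k)/N | upward, or none if k = m |
| Dropped from the analysis | (R − k)/(N − m) | upward if k/m < R/N, downward if k/m > R/N |
| Kept and counted as non-response | (R − k)/N | downward, or none if k = 0 |

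Section 16.2 keeps every dosed patient in the efficacy analysis but does not say which row applies. N is not stated. Even if all of the roughly 20 planned subjects were scanned, one subject wrongly read as a response would move the rate by 1/20, or 5 percentage points. With fewer scanned, the shift is larger.

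**The case against.** The strongest reply is that the plan's intention is plain. Four sections put the scan at Visit 6, and 9.5.1 may be no more than a booking note. A reader might take the Section 26 label as independent permission to scan up to Visit 7. It is not: the row marks Visit 6, and the same label covers Visit 0, where Table 1 requires the scan before the first injection. It more naturally means a radiology appointment around the visit. That part of the reply stands, so the conflict rests on 9.5.1, with the Section 26 label merely silent on a limit.

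It is also fair that 52 days is the outer edge, that alternative treatment is only offered to stable lesions, and that Section 7.4 bars several topical and injectable agents at the study site during follow-up. These points narrow the route without closing it. Table 7 itself gives surgical excision as an example of alternative intervention (for recurrence after complete response), and 7.4 does not bar excision.

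The reply does not remove the problem. Section 9.5.1 is an instruction that staff will follow, and Section 16 has no rule to catch the result.

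**Conclusion.** The point holds as an internal conflict with a real consequence for secondary endpoint 6. Under 9.5.1, the scan can fall nominally up to 42 days, and at most about 52, after the clinical measurement. It can also follow another treatment in TILs without response, most clearly those with stable disease. This assumes that Visit 7 is counted from the actual Visit 6, and that some sites or staff work from 9.5.1. How often it would happen cannot be told from the documents.

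Three stronger readings are not supported:

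- **That the ultrasound rate is biased upward.** The direction depends on how missing and post-treatment scans are counted, which the plan does not say.
- **That the number of subjects affected can be found by applying the non-response share under the 80% design alternative to all 20 subjects.** Only one of two sites scans, its enrolment is not stated, and 80% is a design value. Clinical responders can also disagree with ultrasound, so non-responders do not hold all the discordance.
- **That the main result is at risk.** The primary response rate is clinical and is unaffected, as is the two-stage decision.

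**What to change.** - **Timing.** Bring 9.5.1 and the Section 26 label into line with 9.3 and 9.4.1. Tie the scan to the actual Visit 6 clinical measurement: same day, or within a few stated days. Book it so that it precedes any alternative treatment of a TIL, without changing when that treatment is offered. The visit's own window of 7 days either way is not a sufficient limit, because two dates inside it can be 7 + 7 = 14 days apart. Correct the visit name in 9.4.2 at the same time.
- **Counting rule.** In Section 16, state that a TIL with no scan before alternative treatment is not counted as an ultrasound response and that its subject stays in the denominator. This also covers TILs withdrawn before Visit 6. Say how the sum of diameters is formed when a subject has several TILs and one lacks a valid scan.
- **Sensitivity analysis.** Repeat the analysis in subjects with a valid paired scan, because the main rule can under-count by k/N.

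Optional and separate: a two-by-two table of agreement would suit two yes/no outcomes better than a correlation.

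The cost is wording and less flexible radiology booking. No extra scan or subject is needed.

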2.4 The subject participation time period

The subject participation period will be approximately 48 weeks. This will include a screening visit, 4 injection visits and 5 follow up visits. Total length of study/patient is 8.5 to 10.5 months.

Table 1. Visit Schedule

Screening Visit/V0

Selection of study TILs. Low-risk cSCC with at least 1 lesion > 0.5 cm to < 5 cm. TILs will have partial biopsies for confirmatory diagnosis. A total of up to 5 TILs per subject can be selected for treatment with no more than 3 lesions in one anatomical area. TILs in the same anatomical area will need to be 10 cm apart from the other injected lesions. A high frequency ultrasound of the TILs will be performed at baseline prior to starting first injection.

Selection of study TNILs. Lesions that are clinically suspicious of cSCC in the same anatomical location as TILs. Up to 10 TNILs can be followed with no more than 2 TNILs selected in the same anatomical area as a TIL. TNILs will have partial biopsies for confirmatory diagnosis. TNILs will be assessed by clinical measurement only without the use of ultrasound technique.

Visit 1: First Injection Visit: One to four (1-4) weeks after V0

- Target lesions (TILs and TNILs) are identified and documented with measurements and photographs. Photographs will be taken with regional and close up view of the anatomical area and lesion (Appendix A).
- Inject 0.1ml 4ml (based on TILs size section 7.1, Table 5) Talimogene laherparepvec at nominal concentration of 10⁶ plaque forming units (PFU)/mL with approximately 1.15 mL in a 2 mL vial for the initial dose. This will be administered intralesionally to 1-3 cSCC lesions per anatomical site with a maximum of 5 injectable lesions per patient.

Visit 2: Second injection visit: Three (3) Weeks after V1

- Target lesions are identified and documented with measurements and photographs. Photographs will be taken with global and close up view of the anatomical area and lesion (Appendix A).
- Inject 0.1ml 4ml (based on TILs size) and number of lesions selected.
 Talimogene laherparepvec at nominal concentration of 10⁸ PFU/mL with

approximately 1.15 mL in a 2 mL vial for the second and subsequent doses.

Visit 3: Third injection visit: Two (2) Weeks after V2

- Target lesions are identified and documented with measurements and photographs. Photographs will be taken with global and close up view of the anatomical area and lesion.

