9.8 Off Study

Subjects will be considered off study when all planned treatment, early termination and follow-up visits have been completed, unless death or withdrawal of consent to continue participation occurs.

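### A Visit 8 line in Section 9.5.1 ends participation for disease-free subjects and contradicts the unconditional Visit 9 call; if followed, follow-up for time to progression depends on response status

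*Combined protocol and SAP*

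**What the plan says.** The line at issue is in the Visit 8 list of Section 9.5.1: "If sites are free of disease, participant participation will be complete". The Visit 8 list in Section 9.3 covers the same visit and does not contain it.

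Elsewhere the call carries no condition on disease status:

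- Directly after the Visit 8 list, Section 9.5.1 gives "Visit 9 – Telephone Follow up (356 +/- 31 days) after Visit 1".
- Table 1 in Section 2.4 states the purpose: "Research coordinator will assess patient over the phone to determine if any changes have occurred to target lesions after V8".
- Section 9.3 says what follows from a positive answer: "If active lesion(s) are noted by the participant, they will follow up with a dermatologist and their records will be requested".
- The Section 26 schedule shows the telephone assessment without restriction.
- Section 2.4 counts five follow-up visits, which can only be Visits 5 to 9.
- Section 9.8: "Subjects will be considered off study when all planned treatment, early termination and follow-up visits have been completed", with exceptions only for death and withdrawal of consent.

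On length, Section 2.4 gives about 48 weeks and also "Total length of study/patient is 8.5 to 10.5 months". Table 1 puts Visit 9 at twelve months after Visit 1, whereas Sections 9.3 and 9.5.1 put it at 356 days.

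**The concern.** Someone working from Section 9.5.1 could close out a disease-free subject at Visit 8, especially as the payment form is completed there. Someone working from Section 9.3 would make the call. Section 2.2 names two sites, so practice could differ between them.

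If the line is followed, the call reaches only subjects with residual lesions. For injected lesions still in partial response at Visit 8, Table 7 names that visit as the point "where alternative therapeutic intervention will then be offered". Lesions that are stable with no response by Visit 6 will already have had that offer. The call would then be made largely where a lesion may have been treated another way. It would be omitted in complete responders, for whom recurrence is the question.

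The endpoint at stake is TTP. Sections 3.2, 9.4.1.1 and 16.1.2 run it to the first objectively documented recurrence or progression, with no cut-off at Visit 8, and Section 16.2.5 gives no censoring rule. Durable response, and the six months of follow-up that Table 7 promises for a complete response of an individual lesion, also need observation beyond Visit 8 in some subjects.

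**Working it through.** Inputs are the visit intervals in Table 1, the windows in Sections 9.3 and 9.7, and the Visit 9 timing in Table 1 and Sections 9.3 and 9.5.1. Visit 1 is day 0 and a month is taken as 30.44 days, so six months is about 183 days.

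**The plan's stated length.**
- Visit 8: 21 + 14 + 14 + 28 + 28 + 42 + 98 = day 245 (35 weeks).
- Screening to Visit 8: 245 + 7 to 245 + 28 = 252 to 273 days, or 36 to 39 weeks, 8.3 to 9.0 months. Cumulated windows widen this to 6.4 to 10.8 months.
- Screening to Visit 9: 356 + 7 = 363 days to 365 + 28 = 393 days, or 11.9 to 12.9 months.
- The upper limit of 10.5 months is 10.5 × 30.44 = about 320 days. Even counted from Visit 1, that is before the earliest permitted call, 356 − 31 = day 325. The stated 8.5 to 10.5 months therefore fits an end at Visit 8 and not at Visit 9.
- The other figure, 48 weeks, is 336 days. Counted from Visit 1 it lies inside the Visit 9 window of day 325 to 387, so it does not by itself conflict with Visit 9.

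**Observation lost if the line is followed.**
- Visit 9 at 356 days: 356 − 245 = 111 days; 111/356 = 31% of the time from Visit 1 to Visit 9.
- Visit 9 at twelve months: 365 − 245 = 120 days; 120/365 = 33%.

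**Reach against six months, by the visit at which response is first recorded.**

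| First recorded | Days to Visit 8, nominal | Range with windows | Days to Visit 9, nominal |
|---|---|---|---|
| Visit 4 (day 49) | 196 | 151 to 241 | 307 to 316 |
| Visit 5 (day 77) | 168 | 130 to 206 | 279 to 288 |
| Visit 6 (day 105) | 42 + 98 = 140 | 109 to 171 | 251 to 260 |

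A response first recorded at Visit 6 cannot reach 183 days by Visit 8, even with both later windows at their maximum (140 + 10 + 21 = 171). One first recorded at Visit 5 misses it nominally. Visit 9 clears it even in the tightest case: Visit 6 at its latest, day 128, and the call at its earliest, day 325, are 197 days apart.

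**The case against.** The strongest reply is that this is one stray line against the rest of the document. The same section lists Visit 9 immediately afterwards without a condition, and Sections 2.4, 9.3, 9.8 and 26 all keep it. The line may mean only that clinic attendance ends at Visit 8, which would fit the payment form there and the permission in Section 7.4 to restart systemic agents after that visit. This largely stands. A reader might infer that the design releases complete responders at Visit 8; the documents conflict on this and do not settle it.

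Three further inferences are tempting and are not supported:

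- *Visit 9 is the only source for late recurrence.* It is the only scheduled subject contact. The exploratory chart review of nonmelanoma skin cancers (Sections 9.4.3 and 16.1.3) runs to twelve months after Visit 4, about day 49 + 365 = 414, and to 24 months if available. It could record a recurrence, although it counts cancers and does not assess target lesions.
- *Release at Visit 8 makes TTP look better.* Kaplan-Meier censoring at Visit 8 does not credit event-free time afterwards. Under the line, the later risk set would hold only subjects with residual lesions. Their hazard could be higher, or lower after other treatment, so the direction is open.
- *Duration of response is inflated.* For a complete response without recurrence it is measured at Visit 8 in any case (Sections 3.2, 9.4.1.1 and 16.1.2).

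Visit 9 is also a verbal report, so a recurrence becomes objectively documented only through the records then requested. That limits what the call can show, but is no reason to omit it in disease-free subjects.

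**Conclusion.** The contradiction is real and should be resolved. If the Section 9.5.1 line is applied, each disease-free subject loses 111 to 120 days of observation (31% to 33% of the time from Visit 1 to Visit 9) and the only scheduled contact after Visit 8. TTP follow-up then depends on response status, and late recurrence in complete responders may go unseen. For responses first recorded at Visit 6, no scheduled contact would reach the six months used for durable response and for follow-up of individual complete responses in Table 7.

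The loss is conditional on the line being followed, and the figures assume nominal visit timing except where windows are shown. The primary endpoint at Visit 6 is not touched. The separate mismatches, 8.5 to 10.5 months against a call at about twelve months and 356 days against twelve months, hold whichever way the line is read.

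**What to change.** Delete the line from Section 9.5.1, or reword it so that it ends clinic visits only. State once that Visit 9 applies to all treated subjects who have not withdrawn consent, whatever their disease status at Visit 8. State that a recurrence documented in the records requested at Visit 9 counts for TTP on its documented date; this applies the existing definition.

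In Section 2.4, reconcile the 8.5 to 10.5 months with Visit 9: screening to Visit 9 is about 12 to 13 months. Choose one Visit 9 timing, 356 days or twelve months, and use it throughout.

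The cost is wording plus one telephone call per disease-free subject, in a trial of about 20. The call is already in the schedule, and no treatment rule changes.
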